Official Title: Improving Cardiovascular Risk Factors in Black Young Adults

NCT Number: NCT04412954

Document Date: 12/1/24

The purpose of this randomized controlled trial (RCT) is to demonstrate the efficacy of the investigator developed intervention targeting weight loss through healthy eating and increased physical activity in Black and Hispanic community college students.

2.2 Primary and Secondary Aims

The primary aim (Aim 1) of the Aspire to Better Health study is to test the efficacy of a smartphone app plus health coaching intervention targeting weight loss vs. an attention control condition utilizing a device which tracks sleep.

The secondary aim (Aim 2) is to examine mediating variables of the intervention delivery on percent weight loss at 6 and 12 months. The mediators include adherence to self-monitoring, levels of discrimination, and dietary and physical activity (PA) self-efficacy. Finally, the third aim (Aim 3) will explore potential moderators of percent weight loss at 6 and 12 months, including depressive symptoms, ideal body image, and motivation for behavior change.

2.3 Design

Participants will be randomized with equal allocation to a 12-month intervention that includes using a smartphone app and text messages from a health coach or to an attention-control condition. In total, 256 individuals will be enrolled and randomized with a target of 80% Non-Hispanic Black, 20% Hispanic Black with 50% male representation in each ethnic group. Participants will be enrolled from a community college in Columbus, OH. The intervention will be delivered via a smartphone and the health coach will send the text messages. This study employs an attention-control condition to keep control participants engaged in the study and have them return for data collection visits. Considering the limited number of studies describing recruitment and retention methods for this population, an attention-control condition rather than a standard control condition is warranted. The study was approved by the Institutional Review Board (IRB) at The Ohio State University (OSU).

2.4 Eligibility

Interested participants are instructed to complete an eligibility screening tool they receive via email, or complete a screening call with a trained research assistant to determine study eligibility. The project coordinator or assistant also screens for symptoms of disordered eating in all interested participants, using four behavioral questions from the Eating Attitude Test (EAT-26).¹⁶ If an interested participant answers “yes” to one of four questions, they are not eligible to enroll in the study.

2.5 Inclusion and Exclusion Criteria

Table 1: Inclusion and Exclusion Criteria for the ASPIRE Study	
Inclusion	Exclusion

• Age 17-25• Enrolled in at least 1 CC class	
• Currently pregnant or planning to become pregnant

 • Identify as Black or Hispanic Black • BMI 25 or greater • Own a smartphone (iOS or Android) or compatible device • Ability to return for 12-month visit • Speak and read English 	
 within 12 months • Current participation in another weight loss program or taking weight loss medications or medications known to increase weight • Lost $\geq 10\%$ of body weight in past 6 months • Screens positive for symptoms of disordered eating • Diagnosed with type 1 diabetes
--	---

2.6 Sample Size and Randomization

A sample size of 256 participants (n=128 per each trial arm) will have sufficient power (80%) to detect an

average between-group difference with a moderate effect size of Cohen's $d = 0.4$. The mixed effect modeling for repeated outcome measures at 6 and 12 months was used for the power calculation using two-sided significance level of 0.05 assuming 1) first-order autoregressive covariance structure, 2) the within-structure correlation of 0.8, and 3) 20% attrition rate at 12-month follow-up. After completing the informed consent and baseline data collection, participants will be randomly assigned 1:1 to the intervention or the attention-control group. Stratified randomization by sex (female vs. male) and ethnicity (Non-Hispanic Black vs. Hispanic Black) will be used. For each sex-ethnicity stratum, randomization will occur in permuted blocks of varying block sizes. The advantage of permuted block randomization is that it will ensure balance in the number of participants in the two trial arms during the entire study period.

2.7 Consent

Informed consent will be obtained in a private session by a trained study team member (research coordinator/assistant). Potential participants will be assured that: 1) their participation is voluntary; 2) they are free to withdraw from the study at any time; and 3) if they decline to participate or withdraw

from the study, it will not affect their future care or participation in other activities. For participants under the age of 18, a parent or legal guardian must accompany them to their enrollment appointment. Once the participant is 18 years of age, they will repeat the consent process again at their next in-person visit and sign the relevant form.

2.8 Community Advisory Board

The study convenes a community advisory board (CAB) comprised of faculty, alumni, staff, and current students at CSCC. The CAB is comprised of a diverse group of individuals, most of whom identify as a racial or ethnic minority. The board is also made up of individuals who specialize in student needs, such as mental health counseling and student services. The CAB meets regularly to discuss recruitment standards and methods, intervention methods, current manuscripts and abstracts, as well as ethical standards, and dissemination of findings. The CAB contributes in a meaningful way to the ongoing study by partnering with the research team to contribute new ideas and to create process-related changes necessary for the deployment of a successful project.

3. Program Implementation

3.1 Components of Intervention

Intervention components include the following: 1) access to a smartphone app called Lose It! 2) Health Coach counseling session, 3) Health coach text messages, 4) Fitbit Inspire 2 accelerometer.

3.2 Smartphone Application (Lose It!)

The Lose It! app is a free program, commercially available on both Android and iOS devices. The application is capable of monitoring energy intake, body measurements, and weight loss goals personalized to the participant. The Lose it!! application has previously been examined for behavioral theory content in five distinct categories: knowledge, cognitive strategies, behavior strategies, emotion-focused strategies, and therapeutic interventions. Further, it was ranked number one overall for behavioral theory score and persuasive technology score, and has been successfully employed in a similar study with a racially diverse group of young adults¹⁷. Participants can self-monitor their energy intake by scanning barcodes on food labels or using the large, international database of foods/drinks available on the app.¹⁸ Participants will be given a manual for use of the app.

The smartphone app is associated with a program called Ascend, which provides health coaches access to real-time data from each of their participants, including food intake, calories consumed, macronutrient and micronutrient intake, and physical activity performed. The health coaches use these data to send text messages to participants. All user data are stored on a system with a user identifier and placed in a separate data store. The data stores are hosted in a secure data system with industry standard approaches to access control. Data transfer between participant devices (phone and computer) takes place over an authenticated HTTPS channel. Only the health coach and research staff have access to all participant data.

3.3 Health Coach

Health and wellness coaches have been recruited from the Health and Wellness Innovation in Healthcare Program at OSU and are responsible for delivering intervention components. They are selected as health coaches by the Director of Health Coaches (Investigator [name]) and then interviewed to ensure fit for the

study. In addition to having a healthcare background (ie. registered nurse, patient care nursing assistant, etc.) coaches received training from the principal investigator (PI) and Director of Health Coaches and are continuously monitored throughout the study with in-person meetings with the study PI.

The director of health coaches attends approximately 20% of all baseline coaching sessions to ensure intervention fidelity. The project coordinator and the study PI monitor text messages sent from the health coaches to participants to ensure duplicate messages are not sent and that health coaches are following text message guidelines.

3.4 Counseling Session with Health Coach

Participants in the intervention group are seen for a one-time, 45-minute counseling session at baseline. Due to COVID-19, these meetings will take place via Zoom and all are conducted in English. The counseling will focus on (1) adhering to good nutrition practices, (2) PA guidelines, (3) motivators and outcome expectations for weight loss, (4) goal-setting for diet and PA. Each participant works with their health coach to identify appropriate and individualized goals for energy consumption and physical activity.

3.5 Content of Text Messages from Health Coach

The health and wellness coaches are responsible for electronically monitoring the daily progress of the participant and interact with the participant through push-only text messaging (no response from participant). Health coaches will send one text message per day to each participant. Text messages will not be repeated from the health coach. A database of text messages was created and tested in our previous study and will be used as message stems for the current study. The database contains over 3,000 basic text messages (stems), derived from Social Cognitive Theory, organized by content and mechanism to increase self-efficacy (Table 2). The health and wellness coach will select an area of focus (sodium content, calories, etc.) based on the participant's daily electronic log and select a text message stem and then will personalize that stem based on their client's specific goals or progress for that day. Health coaches also have the ability to create new messages based on the participant's current progress and needs. In addition, due to the ongoing Covid-19 pandemic, health coaches send text messages related to mental wellness and stress management.

Table 2: Example Text Message Stems		
Self-Efficacy Enhancing Mechanism	Content Area	Example Stem
Social Modeling	Physical Activity Motivation	Find a friend that needs or wants to exercise and ask them to take a walk or jog with you today

Verbal Persuasion	Breakfast Consumption	Did you know that people who skip breakfast tend to snack more during the day?
Self-Regulation/Mastery	Cultural Foods	Not finding your homemade family meals on the app? Create your own recipe in Lose it! To help you keep track!
Improving Physical/Emotional State	Body Image Ideals	Find YOUR ideal and work towards it!

3.6 Fitbit

A Fitbit Inspire 2 device will be given to each participant in the intervention group and they will be asked to wear it daily for the duration of the study (12 months). The Fitbit Inspire 2 syncs automatically with the Lose it! App and will update the participant's PA log in real-time. It will also update the participant's daily energy intake needs based on energy expenditure. Health coaches use this adjustment and the real-time PA data for personalization of text messages. Lost or malfunctioning Fitbits are replaced by the study team at no cost to the participant.

3.7 Fitabase

This study utilizes the Fitabase program. Fitabase LLC offers a robust data management platform designed to remotely collect wearable device data. Using Fitabase with wearable devices enables access to daily and intraday data for a variety of tracked types of data including steps, intensity, calories, heart rate

and sleep. This study employs Fitabase to aggregate the active minutes data. Fitbit determines active minutes using a metabolic equivalents measurement ratio (rate of energy expended during an activity: rate of energy expended during rest) that factors in a participant's body mass and heart rate. Fitabase then charts and aggregates this data into categories of light, moderate, and intense minutes. These data are collected for a period of seven days in accordance with their baseline visit, and their 6- and 12-month visits.

Fitabase is a fully hosted, cloud-based software solution that implements robust industry standards to maintain secure databases and keep data private. Fitabase stores information provided to it by the Fitbit Application Programming Interface (API). Data is stored and indexed in the Fitabase SQL Server database in day total, hour, and minute-by-minute intervals. The account for this study is password protected and only the research staff have access to the credentials.

3.8 Attention Control Condition

Participants in the attention-control condition will also receive a Fitbit Inspire 2 device to track their sleep daily for 12 months. The Fitbit app offers sleep quality tracking and enables users to track pertinent sleep statistics. Participants will passively track their sleep daily and can also actively enter items about their day to help understand their sleep habits.

Participants will be asked to wear the Fitbit Inspire 2 on their non-dominant wrist for 7 days continuously for baseline, 6-month, and 12-month data collection. Their data will be automatically downloaded for use by the research team through the Fitabase platform.. At the final 12-month visit, the attention-control group will download and receive a training session on the Lose it! App, as well as keep their Fitbit.

3.9 Systems of Support

Project staff are provided cell phones to enable accessible and timely communication with participants in regarding technological issues, scheduling, and other emergency circumstances. Acknowledging the various social determinants of health that CC students of color experience, project staff have designed an ecosystem of support in collaboration with the community college to enable access to mental and physical health, financial, educational, and housing services if requested by the student. If students screen positively for suicidal ideation on the administered PHQ-9, they are immediately connected to services and study staff follow up with participants until they participate in their first appointment. Additionally, project staff are trained in Mental Health First Aid to equip them with the tools and skills to manage a mental health crisis in a young adult, e.g. recognizing signs and symptoms, how to listen non-judgmentally and give reassurance, and how to refer someone to appropriate services.

4. Measurements

The study team will collect outcome measure data (Tables 3 and 4) from all participants at in-person or Zoom visits at baseline (prior to randomization), 6- and 12-months. The project coordinator and research assistant are not blinded to the treatment condition. At the conclusion of the 12-month visit, participants complete a quality assessment survey to detail their satisfaction with or suggestions for the program.

Table 3: Main Outcome Measures

Outcome	Time Measured	Definition	Measurement Procedure	Measurement Tool
---------	---------------	------------	-----------------------	------------------

Weight	Baseline, 6 and 12 months	Body weight (kilograms)	Wears light clothing, no shoes; 2 measurements taken and averaged	Tanita BS-549 Ironman Scale
Percent Weight Loss	6 and 12 months	Comparison of current weight to baseline weight, then convert to % of baseline weight	Same as above	Same as above
Weight Loss Maintenance	12 months	Sustained weight loss of 5- 10% of baseline body weight OR maintenance of % weight lost at 6-months	Same as above	Same as above
Height	Baseline	Length of individual (meters)	Same as above	Seca 213 portable stadiometer
Body Mass Index	Baseline, 6 and 12 months	Weight to height ratio	Height and weight of participant	Quetelet index (kg/m ²)
Physical Activity	Baseline, 6 and 12 months	Active minutes per day	Wear Fitbit on non-dominant wrist continually except for shower, bath, swimming Staff calculate average active minutes/day over 7 days at each time	Fitbit Inspire 2 
 • High correlation with steps recorded by the Actigraph and the Yamax pedometer. • Reliable and valid device for measuring activity

			point Data collected remotely over Fitbit's open application programming interface	levels (minutes) in young adults.
Diet	Baseline, 6 and 12 months	Compliance with dietary guidelines for Americans	Participant completed Food Frequency Questionnaire (FFQ) at each time point, FFQ analyzed offsite, returned to researchers. Researchers compute Healthy Eating Index (HEI) score	2014 Full-length Block FFQ is converted HEI Score 
 • Reliable and valid in a population >18 years of age, with the FFQ very close to standardized interviewer administered 24-hour food recalls

Table 4: Proposed Mediators and Moderators

Mediator/Moderator Name	Measure Tool and Procedure	Definition	Reliability/Validity
Adherence to Self-Monitoring (mediator)	Health coach tracks through Ascend app using diet entry of 50% or more of caloric intake	Entering at least 50% of caloric goal on at least 80% of days (or 24 days/month)	This method has been used successfully in previous studies. ¹⁹
Dietary Self-Efficacy (mediator)	Dieting Self-Efficacy Scale (DIET-SE)	Examines three factors of a person's belief in their ability to eat in a certain way: (1) high caloric foods, (2) social and internal factors, and (3) negative emotional events.	Internal consistency between 0.82-0.87 in college students. The test-retest reliability of the scales is 0.83 for a 2-3 week interval. ²⁰

Physical Activity Self-Efficacy (mediator)	Self-Efficacy for Exercise scale (14 questions)	Making time for exercise and sticking to exercise.	In a population of adults, the internal consistency was 0.90 and a test-retest correlation was 0.67. ²¹
Discrimination (mediator)	Experiences of Discrimination (EOD) measure	9 item questionnaire measuring exposure to racial discrimination	Confirmatory factor analysis of 0.74 and test/re-test coefficient of 0.70 and validity of $r=0.79$ in a population of African American and Latino adults. ²²
Depressive Symptoms (moderator)	CDE Patient Health Questionnaire for adults (PHQ-9)	10 questions that assess depressive symptoms. Questions are scored on a 0-3 scale. Total scores range from 0 (no depression) to 27 (severe depression).	Reliable and valid in a diverse group of adults over 18, with a Cronbach alpha reported at 0.89 and 0.86 in two studies and a test-retest score of 0.84. ²³
Ideal Body Image (moderator)	Contour Drawing Rating Scale	Contour drawing of graduated sizes, with 9 images for males and 9 images for females. ²⁴ Participants will circle the figure that represents their ideal body image.	Test-retest reliability was confirmed in college students with a reliability rating of 0.78 and validity was confirmed in college students with 95% accuracy in correct ordering of images. ²⁴
Motivation (moderator)	Treatment Self-Regulation Questionnaire (TSRQ)	15 questions to assess diet and 15 questions to assess exercise. The TSRQ measures three	The TSRQ for diet and exercise was proven reliable in a racially/ethnically diverse group of males and females, aged 18+ years,

		types of motivation: (1) controlled, (2) autonomous, and (3) amotivation.	with Cronbach alphas >0.73. ²⁵
Emotional Support (moderator)	NIH PROMIS tool for emotional support (16 questions)	Assesses perceived feelings of being cared for and valued as a person and having confidant relationships	Questionnaire has been validated in adult populations. ²⁶

6. Statistical Analysis

Aim 1: Descriptive statistics will be used to check the distribution of the data, identify outliers, and describe the sample characteristics. Bivariate statistics will be used to compare baseline characteristics between the two trial arms. We will use mixed-effects linear regression modeling for repeated measures to 1) estimate the fixed effects of intervention, time, and their interactions, 2) derive contrast estimates for between-group differences in % weight loss at 6 months and 12 months, 3) adjust for covariates (e.g., any imbalance in baseline characteristics) and within-subject dependency from repeated measures.²⁷ All tests will be performed using Intent-to-Treat (ITT) analysis.

Aim 2: We denote X = Independent variable, Y = Outcome measures, and M = Potential mediator. Mediation will be tested through first showing that X (e.g. intervention) is associated with both M (e.g., dietary self-efficacy) and Y (e.g., % weight change) using mixed-effects regression models as described above. Then, we will sequentially model the effect of X on Y, without and with adjusting for potential mediators. At last, we will use mediation path analysis to simultaneously regress (a) Y on M and X, and (b) M on X.. Estimates for the mediation effect will be derived using delta method or bootstrapping method if lack of normality is evident.²⁸ Adequacy fit of the path model is indicated by a non-significant χ^2 statistic, Comparative Fit Index (CFI) and Tucker-Levis Index (TLI) ≥ 0.9 , and a root mean square error approximation (RMSEA) ≤ 0.08 .

Aim 3: Similarly, we specify X = independent variable (e.g., intervention), Y = outcome variables (e.g., % weight change), and W = potential moderator (e.g., depressive symptoms). We will then test the significance of the moderating effect by including the interaction term of X and W in the mixed-effects regression models. A significant interaction between X and W suggest that the effect of X on Y changes at different levels of W.

Missing data: We will carefully examine the pattern of missing data and conduct appropriate multiple imputation if data are missing at random. If missing not at random is indicated, pattern mixture modeling will be used instead. Sensitivity analysis will be used to evaluate the robustness of study findings under different methods.

7. Data Management

REDCap data collection projects rely on a study-specific data dictionary defined in an iterative self-documenting process. REDCap supports electronic signatures by positively identifying the user through a unique username and password combination. The provisioning of accounts for system authentication is

integrated with the OSU Wexner Medical Center (OSUWMC) LDAP authentication service for studies containing protected health information (PHI) and is secured behind the OSUWMC firewall.

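### The weight loss maintenance rule in Table 3 has an upper limit of 10%, so some participants who keep off more weight are scored as failures

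*Combined protocol and SAP*

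**What the plan says.** Section 4, Table 3 lists the main outcome measures. Percent weight loss at 6 and 12 months is described there as "Comparison of current weight to baseline weight, then convert to % of baseline weight". Weight loss maintenance, measured at 12 months, is a yes/no outcome met by "Sustained weight loss of 5- 10% of baseline body weight OR maintenance of % weight lost at 6-months". The table does not say whether 10% is a cap or an informal target. It gives no minimum for the 6-month loss, no regain tolerance and no rule for people who had lost nothing at 6 months. It also does not say whether *sustained* refers to 12 months alone or to both visits.

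No other section fills these gaps. Section 6 plans, for Aim 1, to "derive contrast estimates for between-group differences in % weight loss at 6 months and 12 months" and names no analysis for maintenance. The aims in Section 2.2 are framed on percent weight loss; Aim 2, for example, is "to examine mediating variables of the intervention delivery on percent weight loss at 6 and 12 months". Section 2.6 bases the sample size on a standardised difference of 0.4, "the within-structure correlation of 0.8" and "20% attrition rate at 12-month follow-up".

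**The concern.** For a given 6-month loss, a success rule should not turn a success into a failure because more of that loss was kept. The upper limit does this. Because the outcome sits among the main measures, a rate by arm may well be reported. An analyst would then have to settle the cap, the tolerance and the meaning of *sustained* with the weights already in hand.

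The second route raises a separate question of interpretation. With no minimum, a participant at 0.5% at both visits counts the same as one at 8% at both visits, so a reader cannot tell what size of loss the rate describes.

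**Working it through.** **The plan's own figure.** The plan gives no figure for maintenance. Its one computed figure is the sample size, which does not use this outcome. Per arm, 2 × (1.960 + 0.842)² / 0.4² = 98.1, so 99. Allowing for 20% attrition, 99 / 0.8 = 123.75, so 124 per arm or 248 in total, close to the stated 256.

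**Cases through the rule** (6-month loss, then 12-month loss; *sustained* judged at 12 months, no tolerance):

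| Case | Route 1 (5–10%) | Route 2 (6-month loss kept) | Result |
|---|---|---|---|
| 12% → 11% | no, above 10 | no, regained 1 | fails |
| 12% → 9% | yes | no | succeeds |
| 12% → 12% | no | yes | succeeds |
| 9% → 6% | yes | no | succeeds |
| 0.5% → 0.5% | no | yes | succeeds |

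The first two rows show the inconsistency and need no assumption about SDs or means. The third shows that the cap is harmless for anyone above 10% who kept the whole 6-month loss.

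**How often it matters.** Inputs from Section 2.6: correlation 0.8. Assumed, because the documents give none: SD s of percent loss 4, 5 or 7 points, equal at both visits; normal losses; three pairs of mean losses m6, m12. Let L6 and L12 be the losses at the two visits.

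- Given L12 = x, L6 is normal with mean m6 + 0.8(x − m12) and SD s√(1 − 0.64) = 0.6s.
- Rule as written: 5 ≤ L12 ≤ 10, or (L6 > 0 and L12 ≥ L6).
- Fails because of the cap: L12 > 10 and route 2 not met.
- Succeeds with a small loss: L12 < 5 and route 2 met.
- Rate as written = P(L12 ≥ 5) − cap failures + small-loss successes.

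Integrating over x gives these percentages of participants, for SD 4/5/7:

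| Mean loss, 6 then 12 months | P(L12 ≥ 5) | Cap failures | Small-loss successes | Rate as written |
|---|---|---|---|---|
| 0 then 0 | 10.6 / 15.9 / 23.8 | 0.1 / 0.5 / 2.1 | 12.5 / 9.5 / 5.7 | 23.0 / 24.8 / 27.3 |
| 4 then 2 | 22.7 / 27.4 / 33.4 | 1.2 / 2.7 / 6.0 | 7.6 / 6.7 / 4.7 | 29.1 / 31.4 / 32.1 |
| 8 then 6 | 59.9 / 57.9 / 55.7 | 9.9 / 12.4 / 15.1 | 4.1 / 4.4 / 3.8 | 54.0 / 50.0 / 44.3 |

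Check of one cell (SD 5, zero means): 15.87 − 0.49 + 9.45 = 24.83, against 24.82 by direct integration. Almost all cap failures are partial regainers; people with no 6-month loss who exceed 10% at 12 months add at most 0.1 point.

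Small-loss successes as a share of all successes at zero mean loss: 12.5/23.0 = 54%, 9.5/24.8 = 38%, 5.7/27.3 = 21%. Successes with under 1% loss are rare: 0.8/0.5/0.3% of participants.

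**With a 1-point regain tolerance in route 2**, cap failures fall to 0.05/0.3/1.6% at zero mean loss and 7/10/12% at 8% then 6%. The case 12% → 11% now passes, but 12% → 10.5% still fails while 12% → 9% passes.

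**Difference between arms** (percentage points, SD 4/5/7, controls at zero mean loss):

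| Intervention arm | Rule as written | At least 5% at 12 months |
|---|---|---|
| 0.4 SD better at both visits | 11.3 / 11.9 / 11.7 | 9.2 / 11.6 / 13.9 |
| 3% then 2% | 10.5 / 9.5 / 6.7 | 12.1 / 11.6 / 9.7 |
| 4% then 2% | 6.2 / 6.6 / 4.8 | 12.1 / 11.6 / 9.7 |

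**The case against.** A reader might infer more than the cap defect: that the second route also misclassifies people, that the reported rate is therefore too high or too low, and that the arm difference is diluted. The documents do not support this. Too high or too low needs a true state to compare with, and no section adopts at least 5% at 12 months as the meaning of maintenance. Crediting people for keeping what they had lost by 6 months is a legitimate meaning of the word. The 5% benchmark is itself closer to a 12-month responder rate. At zero mean loss, 10.6 − 6.0 = 4.6, 15.9 − 9.8 = 6.1 and 23.8 − 15.9 = 7.9 points of its successes (SD 4/5/7) come from people who were under 5% at 6 months.

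Nor is dilution general. With an equal 0.4 SD shift, the rule as written gives no smaller a difference at SD 4 and 5, and a somewhat smaller one at SD 7. Marked dilution needs an intervention arm that loses much more early and then regains a large part. The 4% then 2% path has a 6-month effect of 4/4 = 1.0, 4/5 = 0.8 and 4/7 = 0.57 SD, above the plan's 0.4.

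The wording can also be read more kindly. If 5–10% is an informal target, the cap disappears, but the text does not say so. If *sustained* means within the range at both visits, 12% → 9% fails as well. Yet 12% → 11% still fails while 9% → 6% passes, with less lost at both visits. A regain tolerance shrinks the problem without removing it. Finally, the cap matters most at mean losses near 8%, and nothing in the documents suggests losses that large. These points limit the size of the concern, but the upper limit remains a fault in the stated rule.

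**Conclusion.** The concern holds for the upper limit: as written, the rule can score more retained loss as worse, and no other section repairs it. Under the assumed SDs of 4/5/7 points and the plan's correlation of 0.8, it fails about 0.1/0.5/2% of participants at zero mean loss, 1/3/6% at 4% then 2%, and 10/12/15% at 8% then 6%. These sizes depend on assumed means and SDs; the inconsistency itself does not.

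The missing minimum in the second route is a matter of reporting. One rate combines two constructs, and at zero mean loss about a fifth to a half of successes have under 5% loss. That is not shown to be misclassification, and a general dilution of the arm difference is not shown either.

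Severity is minor. Maintenance is in no stated aim, no named contrast and no power calculation, and the continuous percent weight loss contrasts and the sample size of 256 do not depend on it.

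**What to change.** 1. In Table 3, replace the 5–10% range with at least 5%, with no upper limit.
2. Keep the second route if the sponsor wants it, but report participants who qualify only through it with under 5% loss on a separate line, so that the main rate describes losses of at least 5%.

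In the same edit, clarify whether *sustained* means 12 months only or both visits, how much regain is tolerated, and how people with no 6-month loss are classed. If the arms are to be compared on this outcome, add a line in Section 6 naming the model. The existing intention-to-treat statement and the plan to "conduct appropriate multiple imputation if data are missing at random" can then be applied to the weights from which the outcome is derived.

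The cost is a line or two of text; no new data are needed. The reported rate changes. With *sustained* judged at 12 months, the main rate for SD 4/5/7 would be 11/16/24% instead of 23/25/27% at zero mean loss, and 60/58/56% instead of 54/50/44% at 8% then 6%. People who kept a loss under 5% move to the separate line.

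### The self-monitoring mediator is defined only by a threshold although daily logs are held; the proportion of logged days would keep more information on the adherence-to-weight path

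*Combined protocol and SAP*

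**What the plan says.** - **Role.** Section 2.2 makes adherence an Aim 2 mediator of percent weight loss at 6 and 12 months: "The mediators include adherence to self-monitoring, levels of discrimination, and dietary and physical activity (PA) self-efficacy".
- **Definition.** Table 4 (Section 4) defines it as "Entering at least 50% of caloric goal on at least 80% of days (or 24 days/month"). The procedure column of the same row reads "Health coach tracks through Ascend app using diet entry of 50% or more of caloric intake", so one column refers to caloric goal and the other to caloric intake. The justification given is successful use in previous studies, with a reference.
- **Analysis.** For Aim 2, Section 6 says "we will use mediation path analysis to simultaneously regress (a) Y on M and X, and (b) M on X". M is generic, and the worked example is dietary self-efficacy. Whether adherence is one yes/no, a monthly yes/no, a count of adherent months or a percentage of days is not stated. No sensitivity analysis on the cut-point is named.
- **Data held.** Section 3.2 says that Ascend "provides health coaches access to real-time data from each of their participants, including food intake, calories consumed". Section 3.5 has coaches choose a message focus "based on the participant's daily electronic log".
- **Control arm.** Section 3.8: "At the final 12-month visit, the attention-control group will download and receive a training session on the Lose it! App". Controls therefore have no study diet log during follow-up.

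**The concern.** The 80% rule cannot be applied without first counting valid-log days. The proportion of days is thus an intermediate result that a yes/no variable then throws away. If one yes/no covers the whole period, participants who log on 5% and on 79% of days are treated alike, and so are those who log on 81% and 100%.

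At stake is the path from adherence to weight loss. Because controls have no logs, that path rests on the intervention arm, about 102 people with 12-month data. In a sample of that size, a loss of information can leave a real relation undetected. If the coding is open instead, its form and time window could be chosen after the results are seen.

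**Working it through.** **1. Inputs from the documents.** Section 2.6: 128 per arm, d = 0.4, two-sided 0.05, 20% attrition at 12 months. Completers per arm: 128 × 0.8 = 102.4, about 102.

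**2. The plan's own figure.** Section 2.6 states "A sample size of 256 participants (n=128 per each trial arm) will have sufficient power (80"%). For one visit, the standard error of a standardised difference is √(2/102.4) = 0.1398. Then 0.4/0.1398 = 2.862, and Φ(2.862 − 1.96) = 81.7%, close to the stated 80%. This concerns Aim 1. The documents give no power, adherence rate or distribution for the adherence mediator, so everything below is illustrative.

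**3. Loss from one yes/no cut, normal model.** If a share p is adherent and the relation is linear, the information kept is e = φ(z)²/(p(1−p)), where z is the matching normal quantile. The loss is 1 − e.

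| Adherent | φ(z)² | p(1−p) | Kept | Lost | Sample-size multiple 1/e |
|---|---|---|---|---|---|
| 50% | 0.1592 | 0.25 | 0.637 | 36% | 1.6 |
| 30% | 0.1209 | 0.21 | 0.576 | 42% | 1.7 |
| 20% | 0.0784 | 0.16 | 0.490 | 51% | 2.0 |
| 10% | 0.0308 | 0.09 | 0.342 | 66% | 2.9 |

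The table is symmetric: 70%, 80% and 90% adherent lose the same as 30%, 20% and 10%.

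**4. Other distributions.** A proportion of days lies between 0 and 1, so normality is doubtful.
- Uniform variable: kept = 3p(1−p). The loss is 25% at 50% adherent and 52% at 20%.
- U-shaped variable cut at 0.8: Beta(0.3, 0.3) has 35% adherent and loses 28%; Beta(0.5, 0.5) has 30% adherent and loses 38%.

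**5. If the monthly form is used.** 24 of 30 days is 80%, so the two forms of the rule agree for a 30-day month. Daily logs were simulated with Beta person-level rates, 30-day months and month-to-month variation of SD 0.7 on the logit scale, over 6 and 12 months. Loss is 1 minus the squared correlation with the proportion of days.
- Share of months with at least 24 days: about 13% to 36% lost in scenarios with at least 9% adherent. It is larger, 37% to 63%, in scenarios with under 4% adherent.
- One whole-period yes/no in the same simulations: 33% to 54% lost with 12% to 46% adherent, and about 70% with 9% to 10%.

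**6. Power on the adherence-to-weight path.** Assume n = 102 and a true correlation of r = 0.25. The cut reduces r to r√e, and power ≈ Φ(atanh(r√e) × √99 − 1.96).
- Continuous: atanh(0.25) × √99 = 2.541, power 72%.
- 50% adherent: r√e = 0.199, 2.012, power 52%.
- 30% adherent: 0.190, 1.910, power 48%.
- 20% adherent: 0.175, 1.759, power 42%.

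Direct simulation with 40,000 runs gives 72%, 53%, 48% and 43%. At r = 0.30 the formula gives 87% against 68%, 64% and 56%.

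**The case against.** **The model variable is not stated to be one yes/no.** A reader might infer that the plan commits to dichotomising. It does not: Table 4 gives a definition, Section 6 leaves M generic, and the days-per-month wording permits a monthly indicator that can be summed. This stands. What is firm is that a threshold is the only definition given and that coding and window are unspecified.

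**The size is not a fact from the documents.** A reader might infer that a third to a half of the information is lost. That needs a roughly normal, linearly related variable with about 21% to 79% adherent. Other plausible distributions give less or more, as shown. This stands.

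**Not every cut-off is costly.** If weight loss responded mainly to passing about 80% of days, a cut there could lose little or nothing. So it cannot be said that any threshold has this cost.

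**A yes/no mediator is compatible with the planned path estimate.** A reader might infer otherwise. With randomised X, a linear outcome model and no X-by-M interaction, the linear a-path is the difference in adherence proportions, and the product of paths is still the indirect effect. A simulation returned 0.598 against a true 0.600. Section 6 also allows bootstrapping if normality fails.

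**The remedy leaves the larger weakness.** Without control-arm logs, adherence is undefined or structurally zero in half the sample under either coding. The adherence-to-weight relation remains a non-randomised, within-arm association. This stands.

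**The rule has precedent.** Table 4 cites earlier use. That supports reporting the threshold, but it does not show that the threshold is the better analysis variable when daily counts are available.

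**Conclusion.** The point holds in conditional form. The only stated definition of this mediator is a threshold, finer data are already held for the intervention arm, and no other coding is prespecified.

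If adherence is analysed as one yes/no and the relation is roughly linear, the loss is 36% to 66% under a normal model with 50% down to 10% adherent, and about 25% to 30% for some flatter or U-shaped distributions. Summing monthly indicators reduces it to about 13% to 36% in the scenarios with at least 9% adherent. At an assumed correlation of 0.25 with about 102 completers, the single cut costs some 20 to 30 points of power (72% against 52% to 42%). Adherence rates, distributions, linearity and the correlation are all assumptions.

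The reach is limited to one of the four mediators in a secondary aim. Aim 1 and its stated 80% power are untouched. It is worth changing because it costs almost nothing, not because it threatens the trial's main conclusion.

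**What to change.** In Section 6, Aim 2, prespecify the continuous adherence variable as the proportion of valid-log days up to each visit: months 1–6 for 6-month percent weight loss and months 1–12 for 12-month percent weight loss. Keep the 80%-of-days threshold as a descriptive or secondary version.

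Before that, reconcile the caloric intake and caloric goal denominators in the Table 4 row, because they determine what a valid-log day is.

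The cost is a few sentences in the SAP and a result that is slightly less simple to describe. No new data collection or participant burden is needed. The change does not supply control-arm logs, so the result should be reported as an association within the intervention arm.
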